# 2.3.3 Values below or above a threshold

Safety values expressed as below or above the detection limit will be imputed by the value of the detection limit itself. Listings will always show the non-imputed values.

Total IgG and IgG subtype values expressed as below or above the limit of quantification (BLQ or ALQ, respectively) will not be imputed. For anti-Dsg-1/Dsg-3 autoantibodies, BLQ and ALQ values will be imputed by the value of the detection limit itself. Listings will always show the non-imputed values.

PK concentrations below the limit of quantification (BLQ) will be flagged as such in the listings. For descriptive statistical analysis, all BLQ values will be set to zero. For ALQ values, all ALQ values will be set to the upper limit of quantification for descriptive analysis. Listings will always present the original value.

Anti-drug antibodies (ADA) against efgartigimod: titer of positive ADA samples reported as 'negative titer' will be imputed by 1. Listings will always present 'negative titer'.

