Per parameter and analysis window, the value closest to the target ADY/AWADY will be used in analysis tables and figures, other values will only be listed. If more than one value is located at the same distance from the target, then the latest in time will be selected. The value latest in time will be identified using, in order of preference, the assessment date/time, the visit label or the group identifier (if applicable). For immunogenicity assessments, values resulting in an unevaluable ADA/NAb status are given the lowest priority when the selection is made. For other assessments, missing values are removed before the selection is made.

Partially missing assessment dates disabling allocation to analysis windows will not be imputed and thus these assessments will not be considered in the per-timepoint analysis. Note that these assessments are included in analyses on worst-case.

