# 2.4.1 Calculation of descriptive statistics and percentages

For continuous parameters, full descriptive statistics will only be presented if there are at least 2 non-missing observations. Alternatively, only the number of non-missing data points and mean are shown.

Descriptive statistics will include the number of non-missing data points, the arithmetic mean, the standard deviation (SD), the standard error (SE), the median, minimum, first quartile (Q1), third quartile (Q3), and maximum.

Descriptive statistics for immunogenicity titer values will also include geometric mean (GM) and geometric standard deviation (GSD).

Mean, Q1, Q3, median, GM and GSD will be presented with 1 more decimal place than the measured values, with maximum 4 decimal places. SD and SE will be presented with 2 more decimal places than the measured values, with maximum 5 decimal places. Minimum and maximum will be presented with the same number of decimal places as the measured values, with maximum 3 decimal places.

SGS	Statistical Analysis Plan	
ARGX-113-1905	Final analysis	Final 1.0 of 26APR2024

Descriptive statistics of PK concentrations will include number of non-missing data points, arithmetic mean, SD, median, minimum and maximum, and the coefficient of variation (CV%). The descriptive statistics will be presented with 3 significant digits. If more than half of the values are BLQ, arithmetic mean will be set to BLQ and SD and CV% will not be calculated.

For event-type data, the denominator will be all participants in the analysis set per treatment and phase/period/subperiod (as applicable).

For frequency tabulations and cross-tabulations, the denominator will be all participants in the analysis set per treatment. For tables where results are shown by analysis visit, the denominator will be all participants in the analysis set per treatment and per analysis visit. Missing values will never be included in the denominator count when computing percentages. For cross-tabulations of post-baseline results versus baseline results, a 'missing' category will be shown for baseline results if applicable.

Percentages will be shown with one decimal place.

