## 4.3.2 Derivation rules

Changes and percent changes (compared to baseline, 1904 baseline and TPnB) will be calculated at each analysis visit. See section 2.2.2 for calculation of change and percent change from baseline and TPnB, and section 2.2.4 for the definition of analysis visits overall and by period/subperiod.

Values of anti-Dsg-1/Dsg-3 autoantibodies above or below limit of quantification will be imputed by the upper or lower limit of quantification respectively. This will be explained by a footnote in the appropriate tables. Limits of quantification are provided by the lab. For total IgG and IgG subtypes, no imputation will be applied. Listings will always show the non-imputed values.

For participants with a baseline value below the limit of quantification (BLQ), the parameter will be excluded in presentation of actual values and when computing the change from baseline and the percent change from baseline. This will be explained by a footnote in the appropriate tables.

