### 4.3.3 Presentation of results

All PD endpoints will be summarized by means of descriptive statistics at each analysis visit. Tables will present:

- a) Actual values, changes from baseline and percent changes from baseline by analysis visits overall.
- b) Changes and percent changes versus 1904 baseline by analysis visits overall.
- c) Actual values, changes from TPnB and percent changes from TPnB by analysis visits by period/subperiod.
- d) Changes and percent changes versus 1904 baseline by analysis visits by period/subperiod.

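### Total IgG and IgG subtype results outside the quantification limits have no numeric rule, so any that occur would in practice fall out of the by-visit summaries

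*SAP*

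**What the plan says.** SAP 2.3.3: "Total IgG and IgG subtype values expressed as below or above the limit of quantification (BLQ or ALQ, respectively) will not be imputed". The pharmacodynamics part, SAP 4.3.2, repeats it: "For total IgG and IgG subtypes, no imputation will be applied".

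Every other thresholded result in SAP 2.3.3 receives a number. For the autoantibodies: "For anti-Dsg-1/Dsg-3 autoantibodies, BLQ and ALQ values will be imputed by the value of the detection limit itself". For PK concentrations: "For descriptive statistical analysis, all BLQ values will be set to zero", with ALQ set to the upper limit. Safety values take the detection limit, and a negative ADA titer takes 1.

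On presentation, SAP 4.3.3 says: "All PD endpoints will be summarized by means of descriptive statistics at each analysis visit". SAP 2.4.1 builds such summaries from non-missing points (n, mean, SD, SE, median, quartiles, extremes). When one value per window is chosen, SAP 2.2.4 says of assessments other than immunogenicity that "missing values are removed before the selection is made".

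Exclusion is spelled out for one case only. For a participant whose baseline is BLQ, SAP 4.3.2 says "the parameter will be excluded in presentation of actual values and when computing the change from baseline and the percent change from baseline". SAP 2.3.5 says that all measured results go into the analyses. Limits of quantification are left to the laboratory; neither document gives one for IgG, or an expected share of BLQ results.

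**The concern.** A result held only as less than LLOQ has no number. Without imputation or a censored-data method it cannot enter a mean, median, minimum or change, so it behaves as missing. The loss would not be random: the drug lowers IgG, so BLQ results, if any, should cluster at on-treatment visits with the deepest effect. The tables would then show IgG levels that are too high and a smaller n at exactly those visits.

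Total IgG and IgG1-4 are a secondary PD endpoint (protocol section 3). The protocol describes the pathogenic autoantibodies as mainly IgG4 (2.2 and 8.8.1), so the subtype rows carry clinical interest.

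There is a smaller second route. If BLQ counts as missing in window selection, a quantifiable value further from target could replace it. That needs two samples in one window, which four-weekly sampling makes uncommon outside unscheduled visits.

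**Working it through.** The plan gives no figure to reproduce. The check has two parts: what the rule does, and how large the effect could be.

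**What the rule does.** SAP 2.3.3 and 4.3.2 assign no number; 2.4.1 counts only non-missing points; 4.3.3 asks for descriptive statistics by visit; no censored-data method is named. SAP 2.3.5 asks for every measured value to be included but supplies no value to include. Followed as written, a post-baseline BLQ or ALQ IgG result reaches the listings but not the tables.

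**Size, by hand.** Inputs:
- On-drug mean 35% of baseline, from the 65% maximum mean IgG reduction in the phase 2 ITP trial (protocol 2.3.2). This only sets the scale.
- Log-normal values with CV 0.5 and a BLQ share f = 0.10. Both are assumptions.

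With s = √ln(1 + CV²) = √ln 1.25 = 0.472, z = Φ⁻¹(0.10) = −1.282 and μ = ln 35 − s²/2 = 3.444:
- LLOQ = exp(μ + s·z) = exp(2.838) = 17.1
- Mean with BLQ dropped = 35·Φ(s − z)/(1 − f) = 35 × 0.9603/0.90 = 37.3
- Mean with BLQ set to LLOQ = f·LLOQ + 35·Φ(s − z) = 1.71 + 33.61 = 35.3

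A simulation of 2 million draws gave 37.37 and 35.35. Over CV 0.3 to 0.8, the dropped mean is 36.7 to 38.0 at 10% BLQ and 38.2 to 41.1 at 20%, against about 35.3 and 35.8 to 35.9 with LLOQ.

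**Size, with participant-level baselines.** Assumptions: baseline log-normal with mean 1 and CV 0.6 or 1.0; remaining fraction about N(0.35, 0.10); on-drug value = baseline × fraction. Error in the displayed level, CV 0.6 / CV 1.0:

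| BLQ share | Mean, dropped | Mean, LLOQ | Median, dropped |
|---|---|---|---|
| 5% | +4.1% / +4.7% | +0.3% / +0.2% | +4.0% / +5.7% |
| 10% | +8.1% / +9.5% | +0.9% / +0.7% | +8.1% / +11.8% |
| 20% | +16.3% / +19.8% | +2.7% / +2.2% | +17.2% / +25.0% |

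At 1% BLQ the dropped mean moves by about 1%. With LLOQ substitution the median level is exact while fewer than half the values are BLQ. For scale, 5% BLQ requires an LLOQ at about 5-10% of mean baseline IgG, and 20% requires about 11-17%.

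**Change measures at 20% BLQ, same model:**
- Mean absolute change, in units of mean baseline: true −0.65 to −0.66; dropped −0.72 (CV 0.6) to −0.76 (CV 1.0). Low on-drug values come largely from participants with low baselines and small absolute falls, so losing them exaggerates the reduction.
- Mean percent change: true −65.0; dropped −63.1 (CV 0.6) and −63.7 (CV 1.0); LLOQ −62.5 and −61.7. The errors are 65.0 − 63.1 = 1.9 and 1.3 points when dropped, against 2.5 and 3.3 with LLOQ. Substitution is worse here. At 5-10% BLQ and CV 0.6 it is marginally better.

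**The case against.** The strongest reply is that the SAP says only that these values are not imputed. Where its authors meant exclusion they wrote it, for a BLQ baseline, and SAP 2.3.5 says measured values are included. A reader might infer that the SAP orders post-baseline BLQ values out of the tables; it does not. Exclusion is the natural consequence of having no number, not a stated rule. That distinction stands, but 2.3.5 does not close the gap.

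A reader might also infer that the IgG tables will be biased. The documents do not support that: no LLOQ or BLQ rate is given, and a mean reduction of 65% in another disease says nothing about nearness to an assay limit. Nor is the direction always upward, since the same rule covers ALQ results, whose loss lowers displayed levels.

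Other parts of the reply also stand:
- IgG is not the only marker that can be dropped. The baseline-BLQ exclusion in SAP 4.3.2 covers anti-Dsg too.
- LLOQ substitution does not improve every statistic; mean percent change can be worse.
- On-drug and off-drug rows already differ in participants by design, because treatment stops at CRmin, and subtype testing may be limited to a portion of participants (protocol 8.6).
- No hypothesis is tested (protocol 9.2), IgG tables 14.2.3.1 and 14.2.3.2 are not marked as topline, n is shown, and raw values are listed.

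**Conclusion.** The point holds as a gap in the rule with a conditional effect. Unlike every other thresholded result in SAP 2.3.3, total IgG and IgG1-4 receive no number, so any post-baseline BLQ or ALQ result would in practice leave the by-visit statistics.

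If BLQ results dominate on drug, level summaries are too high by roughly the BLQ share or somewhat less for the mean, and by up to 25% for the median at 20% BLQ; mean absolute change is exaggerated. If none occur, nothing changes. BLQ shares, CVs and the spread of the remaining fraction are assumptions, and the share may differ between total IgG and each subtype.

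It would be wrong to conclude that the drug's percent reduction is materially misreported: in the participant-level model mean percent change moves by at most about 2 points when values are dropped. The gain from a fix lies in levels, medians, absolute change and n. It is a cheap improvement, not a threat to the trial's conclusions.

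**What to change.** In SAP 2.3.3 and 4.3.2, apply the existing anti-Dsg rule to total IgG and IgG1-4 for descriptive statistics: BLQ to LLOQ, ALQ to the upper limit of quantification. Keep raw values in listings.

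In SAP 2.2.4, state that BLQ and ALQ results count as non-missing when the window value is selected. In tables 14.2.3.1 and 14.2.3.2, add n (%) BLQ and ALQ per parameter and visit.

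Keep the baseline-BLQ exclusion in SAP 4.3.2 for change and percent change, but do not let it remove actual values. Baseline is the roll-over value (SAP 2.2.3), which may already be suppressed in participants who received efgartigimod in the antecedent trial.

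The cost is a few sentences, a table row and some programming; no new data are needed. The statistical price is a mean percent change that is conservative by up to about 3 points at 20% BLQ (4.7 points at CV 1.0 if BLQ baselines were not excluded), sometimes worse than dropping. Footnote this, and rely on median levels where BLQ is frequent. A displayed minimum equal to LLOQ should be footnoted as an upper bound.

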# 2.3.4 Rounding of derived variables

Derived variables will be rounded to the appropriate number of decimals at display level:

- Estimated glomerular filtration rate (eGFR) will be rounded to 2 decimals.
- Normalized cumulative prednisone dose (NCPD) and prednisone dose at baseline will be rounded to 2 decimals.
- Cumulative prednisone dose will be rounded to 0 decimals.

# 2.3.5 Outliers

There will be no outlier detection. All measured values will be included in the analyses.

# 2.4 **PRESENTATION OF RESULTS**

Region/country specific outputs will be created to support region/country specific submissions. Specifically, all descriptive outputs described in this SAP will be repeated by region (Japanese / Non-Japanese as defined in the study protocol) to support the J-MAA submission. The definition of a Japanese participant in the protocol is a participant whose parents and 4 grandparents are Japanese, who has the Japanese nationality, was born in Japan, has not lived outside of Japan for a total of >10 years, and currently lives in Japan.

To support the Chinese submission, all outputs described in this SAP will be repeated for the following two subpopulations: Mainland Chinese and East Asian. Mainland Chinese is defined as any participant enrolled by an investigational site located in mainland China and with a race "Asian". East Asian is defined as any participant enrolled by an investigational site located in East Asia (China, Japan), and with a race "Asian". In addition, the Pharmacokinetic and Pharmacodynamics analyses described in sections 4.2 and 4.3 will be repeated for the complement of the Mainland Chinese and East Asian subgroups (i.e. Non-Mainland Chinese and Non-East Asian).

# 2.4.1 Calculation of descriptive statistics and percentages

For continuous parameters, full descriptive statistics will only be presented if there are at least 2 non-missing observations. Alternatively, only the number of non-missing data points and mean are shown.

Descriptive statistics will include the number of non-missing data points, the arithmetic mean, the standard deviation (SD), the standard error (SE), the median, minimum, first quartile (Q1), third quartile (Q3), and maximum.

Descriptive statistics for immunogenicity titer values will also include geometric mean (GM) and geometric standard deviation (GSD).

Mean, Q1, Q3, median, GM and GSD will be presented with 1 more decimal place than the measured values, with maximum 4 decimal places. SD and SE will be presented with 2 more decimal places than the measured values, with maximum 5 decimal places. Minimum and maximum will be presented with the same number of decimal places as the measured values, with maximum 3 decimal places.

SGS	Statistical Analysis Plan	
ARGX-113-1905	Final analysis	Final 1.0 of 26APR2024

Descriptive statistics of PK concentrations will include number of non-missing data points, arithmetic mean, SD, median, minimum and maximum, and the coefficient of variation (CV%). The descriptive statistics will be presented with 3 significant digits. If more than half of the values are BLQ, arithmetic mean will be set to BLQ and SD and CV% will not be calculated.

For event-type data, the denominator will be all participants in the analysis set per treatment and phase/period/subperiod (as applicable).

For frequency tabulations and cross-tabulations, the denominator will be all participants in the analysis set per treatment. For tables where results are shown by analysis visit, the denominator will be all participants in the analysis set per treatment and per analysis visit. Missing values will never be included in the denominator count when computing percentages. For cross-tabulations of post-baseline results versus baseline results, a 'missing' category will be shown for baseline results if applicable.

Percentages will be shown with one decimal place.

#### 2.4.2 Presentation of treatments

The following treatment labels will be used in the tables and listings:

- EFG PH20 SC
- PBO PH20 SC EFG PH20 SC
- Total EFG PH20 SC

## 2.4.3 Ordering in tables, listings and figures

All tables and figures will be presented per treatment and total, unless specified otherwise. In by visit displays, worst-case will be shown last, if present.

In listings for general characteristics, results will be ordered by treatment and participant, unless specified otherwise.

All other listings will be ordered by treatment, participant, analysis visit and time point, unless specified otherwise.

Safety assessments during the roll-over phase will not be tabulated, unless specified otherwise. These assessments will be included in listings, ordered by treatment, participant and time point.

In tables showing several parameters, each parameter will begin on a new page and parameters will be sorted alphabetically, within the parameter category if applicable.

Treatment columns will be ordered in the same order as mentioned in section 2.4.2.

# 3. GENERAL CHARACTERISTICS ANALYSES

General characteristics data will be presented for the Roll-over set with the exception of treatment discontinuation data, concomitant therapy data and IMP administration data, which will be presented for the Safety analysis set.

[figure not shown]
# **3.1 PARTICIPANT DISPOSITION**

The following participant data will be tabulated:

- The number of participants in each analysis set (for all participants (PV+PF) and for PV participants)
- The number of participants per disease status at roll-over from 1904: CRmin, CR, DC - no CR, treatment failure, flare after CRmin (for all participants (PV+PF) and for PV participants).
- The number and percentage of participants by country and site.
- The number and percentage of participants for each analysis visit within
  - The treatment and follow-up phase (as defined in Table 3)
  - Each phase/period/subperiod (as defined in Table 5)
- Descriptive statistics of the phase/period/subperiod duration, calculated as end date start date + 1 day. The following will be presented:
  - Roll-over phase duration
  - Treatment phase duration
  - Follow-up phase duration
  - Each treatment period duration
  - Each subperiod duration within each treatment period
  - Total duration of all on-treatment subperiods (participants without any on-treatment subperiod have a total duration = 0)
- The number and percentage of participants who completed or discontinued the study as documented on the study termination page and the number and percentage of participants for each study discontinuation reason.
- The number and percentage of participants who completed or discontinued the treatment as documented on the end of treatment page and the number and percentage of participants for each treatment discontinuation reason (overall and by disease status at roll-over in 1905 for all participants (PV+PF) as well as for PV participants).
- The number and percentage of participants with minor and major protocol deviations.

All information collected in the CRF concerning study and treatment discontinuation and information on phases will be listed. All minor and major protocol deviations will be listed.

Document template OTH.STAT.010 v3

## **3.2 DEMOGRAPHIC AND OTHER BASELINE CHARACTERISTICS**

# 3.2.1 Available data

The following parameters will be available:

- Demographics: sex at birth, age at informed consent, race and ethnicity (if collection permitted), childbearing potential, height at baseline, weight at baseline, year of birth, date of signing ICF (listed only), country
- Baseline disease characteristics: pemphigus type (vulgaris/foliaceus) and subtype (mucosal-dominant / mucocutaneous / cutaneous) (from 1904), PDAI activity score and PDAI total score at baseline, ABQOL total score at baseline, anti-Dsg antibodies (aDsg1 only, aDsg3 only, both aDsg1 and aDsg3) and prednisone dose at baseline

# 3.2.2 Derivation rules

The following parameters will be derived:

- Region: country will be categorized into the following regions: North America (USA), Europe (Bulgaria, France, Hungary, Germany, Greece, Italy, Poland, Romania, Spain, UK), Asia (China, India, Japan), Rest of world (Australia, Georgia, Russian Federation, Serbia, Turkey, Ukraine)
- Disease severity: PDAI activity score will be categorized into the following disease severities: <15 (mild), 15-44 (moderate), ≥45 (severe)
- Prednisone equivalent dose at baseline (mg/kg/day) = normalized prednisone equivalent dose as detailed in section 3.4.2 of prednisone (actually) administered on the day of the roll-over visit.
   Posults will be rounded as detailed in section 2.2.4

Results will be rounded as detailed in section 2.3.4

# 3.2.3 Presentation of results

Demographics will be presented using descriptive statistics for age, height, weight and BMI, and frequency tabulations for sex, childbearing potential, race, ethnicity, and region.

Baseline disease characteristics will be presented using descriptive statistics for PDAI activity and total score at baseline, ABQOL total score at baseline, prednisone equivalent dose per body weight at baseline (mg/kg/day) and prednisone equivalent dose at baseline (mg/day), and frequency tabulations for all other parameters.

Tables to be produced for the topline results (see list of outputs in section 8.1) will be presented overall and by disease status at roll-over in 1905. These tables will show data for PV+PF participants as well as for PV participants.

All demographic data and baseline disease characteristics will be listed.

# **3.3 PRIOR AND CONCOMITANT THERAPIES AND PROCEDURES**

# 3.3.1 Available data

All therapies are coded using WHO-DD. Anatomical-Therapeutic-Chemical (ATC) selection is performed to select the most appropriate medication class. For the

SGS	Statistical Analysis Plan	
ARGX-113-1905	Final analysis	Final 1.0 of 26APR2024

selected class, ATC coding up to level 4 is available in the clinical database. For each therapy, a start date or prior flag and stop date or ongoing flag are collected.

Procedures are coded using the medical dictionary for regulatory activities (MedDRA) into preferred terms. For each finding, the indication and a start and stop date are collected.

Coding of therapies and procedures will be performed using the latest versions of the dictionaries available at the time of the 1904 study database lock.

